
Additional covariates. Demographic and clinical characteristics as well as information about healthcare utilization and medical technology updates will be assessed by chart review and/or self-report including the participant's diagnosis date, insulin regimen, use of CGM, comorbidities, insurance coverage, medications, and other patient demographics. We will assess family size, parent employment, education, race/ethnicity, insurance coverage, and other socio-economic indices through the baseline questionnaire. Patient and parent demographics will be collected at baseline only, and medical technology changes relevant to diabetes management will be assessed every 3 months.

Protocol Version Number: 10
Protocol Version Date: 7/28/2021

Time from previous PRISM session	Within 4 weeks of enrollment	2-4 weeks 2-4 weeks		Every 2 weeks after PRISM 2 through the end of month 3	Once a month (Months 3-6)		
Session Schedule (PRISM Group only)	PRISM 1	PRISM 2	PRISM 3	Boosters	Boosters		
Time from		0.14		0.84	. 0	9	12
enrollment	0	3 MC	onths	6 Mor	ntns	Months	Months
Survey Schedule (both arms)	Survey	Sur	vey	Surv	rey	Survey	Survey
A1C (both arms)	At-Home Test Kit (if not in Chart)	From Chart	(If Available)	At-Home Tes in M	•	From Chart (If availab le)	At- Home Test Kit (if not in Chart)
Medical Record AbstractionContinuous Glucose Monitoring (GCM) and A1C as Available							

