Medical record data: RAs will collect and upload CRF data quarterly during the 12 months the patient is on study and will include a CRF for the previous diabetes-related visit in closest proximity to the date of enrollment (in instances in which the patient is not seen by a provider during the enrollment period). To ensure reliability and validity of abstracted medical record data, we will use our current methods for training and quality control, including guided practice abstraction and independent abstraction with reconciliation by a medical Co-I ([name]/[name]). A 10% random sample will be dual abstracted.

6. Data and Biospecimen Banking¹²

- **6.1.** Complete list of the data and/or biospecimens to be included in the bank:¹³ Surveys, CRFs (e.g., medical record data), a1c results, and audio transcriptions will be coded and labelled with study ID numbers by the study team.
- **6.2.** Location of data and/or biospecimen storage:¹⁴
 All will be stored in original (hard copy) forms in locked cabinets (where relevant) and/or password-protected secure databases (for all electronic survey data). At-home test kit A1c data will be stored per laboratory protocols at each respective institution.
- 6.3. List of those with direct access to data and/or biospecimens in the bank: Data will not be shared outside the group of investigators conducting the study at SCH and BCM/TCH. When other investigators are interested in new analyses, the PIs will verify they have IRB approval to conduct additional analyses and will be added to the study team. Coded study data will be banked indefinitely for future use by the group of investigators conducting the study and access will be controlled by the PI's. Future studies will formally test the dissemination and implementation potential of the intervention once its efficacy is confirmed.
- 6.4. Length of time data and/or biospecimens will be stored in the bank: Original surveys will be saved for 10 years or until final analyses are completed, whichever occurs last, in order to ensure data quality. Coded electronically saved study data will be banked indefinitely for future use by the group of investigators conducting the study and access will be controlled by the Pls.
- 6.5. Procedures for protecting the confidentiality and privacy of the subjects from whom the data and/or biospecimens were collected:¹⁵
 Per 6.1, all banked data will be coded and labelled with only study ID numbers, not identifying information.

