 kits. When doing a needle poke, some people may get a small bruise that will go away in
 a day or two. Some people may feel dizzy or faint. There is also a very small chance that
 the patient could get an infection where the needle pokes the skin. These risks will be
 outlined in the consent documents and potential participants would be made aware of
 these risks during the consent conference.
- **PRISM.** The intervention ("Promoting Resilience in Stress Management", PRISM) and our surveys may address sensitive matters in that it they patients to identify stressors and negative thoughts. Adolescent participants may be prompted to think about the threat to their future posed by their diabetes. During the coming together session and/or while completing surveys, parent(s)/caregiver(s) may be prompted to think about the threat to their child's future by diabetes. The topics to be covered may provoke sadness, anxiety, depression, fear or doubt for adolescents and/or their parent(s)/caregiver(s). Administrators of the intervention will be trained to immediately inform the patient's primary social work and/or medical teams if the patient and/or parents/guardians endorses thoughts of self-harm or harm to others, per the clinic policy for responding to suicidal ideation. As part of their informed consent process, participants will be made aware of this policy, as well as the fact that confidentiality may be broken in the case that providers see an immediate threat to the patient's or another's safety. No physical risks are expected to arise from the study.

The primary risk to participants will be concerns about confidentiality, and stress of discussing the topic of their or their child's diabetes experience. While the potential risks to participants are low, we will take steps to ensure that all potential risks are handled appropriately as described below.

Due to the nature of the PRISM intervention, all staff and participants will be unblinded from the time of randomization.

Protocol Version Number: 10
Protocol Version Date: 7/28/2021

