16.2. Data reviewed to ensure safety of subjects:

DSMC members will provide input and feedback to the PI and Co-investigators, via e-mail and conference calls, related to (a) accrual rate, (b) study eligibility determination issues, (c) data completion rates including conformance with informed consent requirements, (d) intervention fidelity indicators, (e) adverse events, and (f) compliance with data management procedures. [name] (lead statistician) will oversee the summarization of online data to evaluate data completeness and protocol adherence. The Lead CRA will also send semi-annual reports summarizing recruitment and other site specific data (such as indicators of intervention delivery, occurrence of adverse events, and conformance with IRB requirements).

The committee will also receive information on questionnaire data, presented for the participants overall rather than by study group. This study will not have pre-set stopping rules, but the DSMB will have the option of requesting the data be unblinded and considering altering the study or

Protocol Version Number: 10
Protocol Version Date: 7/28/2021

stopping the study early. Although the full committee will meet twice-yearly, the PI or any member of the DSMB will be free to request to assemble the full committee at any time. Because committee members may be located at various sites, the committee meetings may be conducted by phone.

Data safety monitoring for the intervention will focus on assuring that subjects are not experiencing any significant or unexpected distress and that they are satisfied with the intervention components; we will monitor all complaints about the study. We do not anticipate stopping the study early for efficacy or harm, but the DSMB will have the option to consider such action in the event of a highly unexpected result. The DSMB will review the draft questionnaires to be sent to subjects and review any complaints that may be received from patients, family members, clinicians, or others. We do not anticipate any external factors such as findings from ongoing trials that will affect the safety of participants or the ethics of this research study.

16.3. Safety information collection procedures:

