The DSMB, Lead RA and study team will regularly assess confidentiality of study participants. The following will be assessed and verified: All data will be maintained on secure computers in locked offices at Seattle Children's Research Institute (data collection center); the participant (and caregiver) has signed informed consent and HIPAA forms; all standard confidentiality/privacy rules and guidelines set by the Seattle Children's Research Institute are in compliance. A Certificate of Confidentiality will be obtained.

16.4. Frequency of cumulative data review:

The committee will be convened at the beginning of the study and then twice annually via conference calls, to provide input and guidance on the study evaluation and intervention protocols, including quality assurance and safety issues related to the protocols, as well as data handling activities.

16.5. Conditions that trigger an immediate suspension of the research:

Given the non-invasive nature of our proposed behavioral intervention and based on prior pilot studies,^{30,32} we expect minimal side effects and safety concerns as a result of the PRISM intervention. Thus, there are no pre-planned stopping rules for adverse events since these are not anticipated.

17. Use of Social Media

- **17.1.** Types of social media to be used and how:
- **17.2.** Measures in place to protect the privacy or confidentiality of subjects:³⁷
- **17.3.** Types of communications that will be submitted to the IRB for review:³⁸ n/a

Protocol Version Number: 10
Protocol Version Date: 7/28/2021

17.4. If user-generated content will be active, how it will be monitored and what actions will be taken to ensure subject safety and study integrity:

n/a

18. Research Related Injury³⁹

18.1. Available compensation in the event of research related injury: There is no compensation for research-related injury.

19. Recruitment Methods⁴⁰

19.1. When, where, and how potential subjects will be recruited:

Recruitment and retention will be promoted through a combination of clinic-based approaches and strategies we have successfully used previously.

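### Adverse events are promised to the monitoring committee, but no stated procedure gathers them, and the one trained self-harm disclosure route runs through PRISM staff, so disclosed harms may be captured unequally by arm

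*Combined protocol and SAP*

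**What the plan says.** Section 16.2 lists adverse events among the matters on which the committee advises. It adds semi-annual reports covering items such as "indicators of intervention delivery, occurrence of adverse events, and conformance with IRB requirements". It also says that unexpected distress and complaints will be watched, and that the committee may ask for unblinded data and consider stopping the study.

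Section 16.3 is headed as the safety information collection procedures. Its content is secure storage, signed consent and HIPAA forms, privacy rules and a Certificate of Confidentiality. It opens: "The DSMB, Lead RA and study team will regularly assess confidentiality of study participants". Section 16.5 adds that "there are no pre-planned stopping rules for adverse events since these are not anticipated".

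The response to disclosed self-harm is in section 12.1, under the PRISM risk: "Administrators of the intervention will be trained to immediately inform the patient's primary social work and/or medical teams". The same section says that staff and participants are unblinded from randomization.

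Chart data are planned for all participants. Under Additional covariates, section 5.3 says that "information about healthcare utilization and medical technology updates will be assessed by chart review and/or self-report". Section 5.4 says that "RAs will collect and upload CRF data quarterly during the 12 months the patient is on study". Section 14.2 gives a different interval for the same upload, anywhere from two weeks to six months.

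**The concern.** The committee is promised adverse events, but the section that should say how they are obtained does not do so. Without a stated definition, source, schedule or person responsible, capture is passive: events are recorded when someone happens to hear of them. In this trial the chance of hearing differs by design, because PRISM participants talk with an interventionist over six months and usual-care participants do not.

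The population is adolescents selected for high diabetes distress, and section 12.1 itself expects that the topics may provoke sadness, anxiety or depression. If the committee or the final report compares harms by arm, an excess under PRISM could come from closer observation, or a real excess could be dismissed as that. The analyst cannot repair this later, because events that nobody recorded cannot be recovered from the trial data.

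**Working it through.** There is no stated figure to reproduce. The check is a reading of the routes, a count of contacts, and an illustration.

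**1. Routes by which a harm could become known**

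| Route | Section | Arms | Described as adverse-event collection? |
|---|---|---|---|
| High distress or depression scores may be shared with the clinic team | 12.1 | Both | No |
| Alert for a research at-home A1C above 14% | 12.1 | Both | No |
| Complaints reviewed by the committee | 16.2 | Both | No |
| Unanticipated risks that come to staff attention | 12.2 | Both, passive | No active step |
| Chart abstraction, including healthcare utilization | 5.3, 5.4, 14.2 | Both | No, listed as covariates and medical record data |
| Self-harm disclosed to intervention staff | 12.1 | Scheduled contact in PRISM only | No, a clinical escalation |

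No row defines an adverse event or says who asks about it and when. The heading for safety endpoints (3.2) is not legible in the text available, so nothing is inferred from it.

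**2. Scheduled PRISM-only contacts by month 6**

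Inputs: three sessions 2 to 4 weeks apart. The first falls within 2 weeks of enrollment (5.2) or within 4 weeks (schedule table in 5.3). Boosters follow every two weeks to week 12, then three monthly boosters in months 4 to 6.

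Total = 3 sessions + b + 3 monthly boosters, where b is the number of two-week steps up to week 12.

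- Boosters after session 3 (5.2), fastest: session 3 at week 0 + 2×2 = 4, b = (12 − 4)/2 = 4, total 10.
- Boosters after session 3, slowest under the table: session 3 at week 4 + 2×4 = 12, b = 0, total 6. With a first session by week 2: session 3 at week 10, b = 1, total 7.
- Boosters after session 2 (schedule table): fastest, session 2 at week 2, b = 5, total 11; slowest, session 2 at week 8, b = 2, total 8.

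So there are 6 to 10 contacts, or 8 to 11 on the table's booster rule. Usual care has none of these. Both arms share five surveys (baseline, 3, 6, 9 and 12 months).

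**3. What unequal detection could do (assumed rates)**

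The documents give no incidence or detection rate. With the same true risk p and n per arm, expected recorded events are n × p × d, where d is the share detected. The apparent ratio is d(PRISM)/d(usual care), whatever p is. With n = 80 to 88 (section 5.1) and p = 5%:

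| Detection, PRISM / usual care | Recorded events, PRISM | Recorded events, usual care | Ratio |
|---|---|---|---|
| 60% / 60% | 2.4 to 2.6 | 2.4 to 2.6 | 1.0 |
| 90% / 50% | 3.6 to 4.0 | 2.0 to 2.2 | 1.8 |
| 80% / 40% | 3.2 to 3.5 | 1.6 to 1.8 | 2.0 |
| 80% / 20% | 3.2 to 3.5 | 0.8 to 0.9 | 4.0 |

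For p = 2% the 80%/40% row gives 1.3 to 1.4 against 0.6 to 0.7 events; for p = 10% it gives 6.4 to 7.0 against 3.2 to 3.5. The ratio stays at 2.0.

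**The case against.** The trial is described in 16.1 as no more than minimal risk, and the template's note says section 16 applies to studies above that level, so a thin 16.3 is partly explained. Both arms have depression screening and access to social work in usual care (5.2). Usual-care families also hear from staff: visit reminders (5.4), calls about missing survey items (14.2), and repeated requests for surveys and kits (11.3). The self-harm instruction is a clinical escalation, and nothing says that it feeds a harms count. No section plans a by-arm harms table.

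Much of this stands, and it rules out stronger readings. A reader might infer that every detection route depends on staff contact, or that usual care has no staff contact at all. Neither is so. A reader might also infer that diabetes emergencies go uncollected. The documents do not support that: healthcare utilization is abstracted in both arms and could include emergency visits and admissions, and the form that would settle it is not reproduced. The supportable statement is that the protocol text does not name these events and does not route chart findings to the committee as adverse events. Nor can one infer a doubling of the apparent risk under PRISM; that figure is only the ratio of two assumed detection rates, and the expected counts are small.

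The objection does not remove the gap between 16.2 and 16.3. The routes common to both arms narrow the inequality, but none asks about adverse events. Low expected risk does not help either, because a conclusion of no excess harm also needs equal ascertainment.

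**Conclusion.** The point holds in a limited form and should be acted on. The certain part is that adverse events are promised to the committee and no readable section says how they are gathered. The probable part is that disclosed or spontaneously reported harms, self-harm above all, are more likely to become known in an unblinded arm with 6 to 11 extra scheduled contacts than in one with none. This does not extend to survey scores or A1C, which are collected alike in both arms.

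The size is unknown. The range of 1.0 to 4.0 rests wholly on assumed detection rates and equal true risk; it shows direction and is not a forecast. The conclusion also assumes that the unseen case report form does not already carry a fixed event list. If it does, the remaining work is to say so in 16.3 and state how the events reach the committee.

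**What to change.** In section 16.3, add a fixed, dated event list to the existing chart form: ketoacidosis, severe hypoglycaemia, emergency visits and hospital admissions, and self-harm or psychiatric emergencies. Abstract it identically and on the same schedule in both arms, and base any by-arm harms summary on it.

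Record how each event first became known. Events learned only in PRISM sessions or boosters should go to the committee in full, since session-provoked distress is the most plausible harm of the intervention, but should be tabulated apart from the between-arm comparison. The source field also matters because a disclosure passed to the medical team under 12.1 may then appear in the chart, so the chart list reduces the contact effect for self-harm but may not remove it.

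Reconcile the abstraction interval: quarterly in 5.4 against two weeks to six months in 14.2. A common schedule cannot be claimed while both stand.

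The cost is a few fields in an abstraction already planned, a short addition to 16.3, and some added abstraction time. No clinical response changes.

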19.2. Steps that will be taken to protect potential subjects' privacy interests:41

A variety of measures will be utilized to ensure participant privacy. We will follow standard processes for approach by using letters and/or working with the diabetes provider team to approach in person. Minimal paper records, such as consent forms, will be kept in a locked drawer in the site PIs' research offices. Surveys will be done either electronically via RedCap or mailed to participants based on their preferences. A1c athome test kits will follow clinic and laboratory protocols as defined by each institution and overseen by laboratory directors at each respective institution ([name] & [name]).

19.3. Sources of subjects:42

We will recruit from the diabetes clinics at Seattle Children's Hospital and Texas Children's Hospital.

19.4. Methods that will be used to identify potential subjects:

RAs at each site will screen patients via review of the clinic lists, communication with clinicians, and review of internal databases, followed by a medical chart review to verify eligibility.

- **19.5.** Materials that will be used to recruit subjects:⁴³

 Recruitment letter and flyer are included in the submission materials.
- **19.6.** Recruitment methods not controlled by Seattle Children's:

 There are no study wide recruitment methods (e.g., call centers or national advertisements).

20. Consent/Assent Process

20.1. Consent process overview:44

RAs will conduct in-person recruitment in clinic waiting rooms, at clinic visits and/or inpatient hospital rooms. Consent discussions may also occur by phone/video. Phone/video (via

Protocol Version Number: 10
Protocol Version Date: 7/28/2021

WebEx, Zoom, or Skype) consents will be used in instances where patients are coming to main hospital clinics infrequently (e.g., every 6 months; not coming in for clinic visits due to COVID-19 clinic restrictions). In sum, allowing phone/video consents is necessary for maximizing recruitment and accommodating all diabetes patients, especially in the era of the COVID-19 pandemic. Some patients come to clinic once every 3-6 months, and clinic visits have become less frequent due to increased infection risk as a result of COVID-19. In these instances and in the current circumstances, it is sometimes impossible to ensure that an in person consent conference occurs if a study team member is not allowed to be in clinic due to institutional safety protocols (e.g., COVID-19 restructions), out for the day or if our team has a scheduled meeting. Even if a study team member is able to be at the hospital, there are a number of factors that may preclude an approach in person, especially in the era of COVID-19. Providers may interrupt the consent conference, staff may advise us that the day is not "good" for the family to be approached, illness status may preclude the patient from being cognitively able to provide consent/assent that day, or patients/families may not be presenting in person in clinic due to COVID-19.

The RA will contact families and ask if they are interested in learning about a research study. The consent meeting between the RA and eligible participants (with parents if applicable) will include an explanation of the study in developmentally appropriate laylanguage.

For Phase 1 (Screening), participants will provide either written informed consent (if aged 18 years) or assent (if <18 years-old) if seen in-person or verbal consent (if aged 18 years) or assent (if <18 years-old) if screened by phone/video. Parents of teens (<18 years-old) will provide written informed consent if the patient is seen in clinic or verbal consent if screened by phone/video.

For Phase 2 (Full Study), all participants approached in-person will provide either written informed consent (if aged 18 years) or assent (if <18 years-old). Parents of teens (<18 years-old) approached in-person will provide written informed consent. When the consent conference is conducted by phone/video, those who agree to participate will complete an electronic consent form via the REDcap database using the REDCAP e-consent framework. Study staff may also e-mail a copy of the consent form to subjects if requested. The body of the consent form will be identical, whether on paper or in REDCap. A link to the electronic consent form will be e-mailed to participants prior to the phone/video consent conference. A short code will be generated through REDCap to confirm and verify the identity of the person consenting at BCM/TCH. Study staff will answer any questions about the study, and those who agree to participate will provide an electronic signature, date, and time on the REDCap form to indicate their consent. The REDCap e-consent framework allows participants to create an electronic signature using their cursor and provides a timestamp. This framework also automatically generates an extra certification page for participants to confirm the correctness of their responses before submitting and stores a static copy of their responses as a PDF in the study file's repository. Subjects will also be prompted to download a copy of their signed consent form from REDCap or study staff can e-mail the signed form.

After conducting the consent conference either in person or by phone/video, RAs will create a consent process note for REDCap and the EMR. Included in this note will be the date of

Protocol Version Number: 10
Protocol Version Date: 7/28/2021

the consent conference, the names of the patient and parent (if applicable), the name of the person obtaining consent, the fact that the subject agreed to participate and that all risks and opportunities of the study were explained, and that the subject had adequate opportunity to have their questions answered. If an interpreter is used, the name of the interpreter will be documented.

Consent conferences will not be recorded. Study staff will use a guide for consent discussions over phone/video.

After fully enrolled participants turn 18, they will complete a new informed consent form to continue participation in the study either in-person (as is possible) or via REDCap.

As described in the inclusion/exclusion criteria above, adolescents must speak English fluently; however, they are eligible if English is not their primary language spoken at home (or if it is not their first language). In cases where parent consent is required and parents do not speak English fluently (or prefer another language), all conferences will be held with a trained phone or in-person medical interpreter. All participants and parents will be provided an opportunity to read the consent/assent forms in their preferred language (English or Spanish), to ask questions about the study and have those questions answered by the research team member before deciding about study participation and signing the consent/assent form. Parental permission for study participation will be obtained first then patient assent will be obtained for all patients 13-17 years of age. If a patient indicates that they do not want to participate in any phase of the study that non-assent will override the parent's permission and the patient will be recorded as a refusal. The research team member will redirect any parent who attempts to convince their child to participate in the study and remind them of their child's right as a potential research participant to refuse participation without coercion. Consent to study participation will be obtained from patients 18 years of age and above. The RA will emphasize to all patients and parents in developmentally appropriate lay-language that being in the study is their choice that they may choose not to participate or may change their mind at any time and it will not affect how their nurses or doctors care for them.

Parent/guardian separate consent will be obtained because parents will be completing their own study activities and will be disclosing their own financial information in surveys. At the time of consent, the study activities associated with each arm of the study (surveys for both groups and 'Coming Together' for parents/guardians whose child is randomized to PRISM) will be presented, and parents can indicate on the consent which component(s) they are interested in participating in (with the knowledge that they will not be offered the 'Coming Together' session should their child be randomized to control/usual care). Again, parents/guardians whose child is randomized to control/usual care arm will be eligible to take surveys but will not have the option of the 'Coming Together' visit (as it is a part of the PRISM intervention). Parents/guardians whose child is randomized to the PRISM arm of the intervention may choose to be involved in the 'Coming Together' portion of the study and not want to complete questionnaires and visa versa, they may choose to complete questionnaires and not participate in the 'Coming Together' portion of the study either by their or the patient's choice. It is clearly delineated on the parent consent forms both a) that the parent should indicate which component(s) they are choosing to participate in (if eligible)

Protocol Version Number: 10
Protocol Version Date: 7/28/2021

and b) that the 'Coming Together' session is only offered if the adolescent is randomized to PRISM.

Screening Procedures (Phase 1):

During each consent conference at BCM/TCH, where distress screening (PAID-T) is not standard of care, and for consent conferences at SCH in which the patient has not been administered a PAID-T, we will emphasize that they will need to complete a screening consent form or information sheet (Phase 1) and a brief measure (PAID-T) in order to determine eligibility (see Figure 2 below). If they meet eligibility criteria, they will proceed to Phase 2 of Consenting and will subsequently complete the baseline instruments and will not be given the PAID-T again (i.e., the PAID-T score from screening will count as their baseline PAID-T value). If they do not meet eligibility criteria, we will thank them for their time and confirm they are not eligible for the study. If they are eligible and interested in the study, we will ask them to complete the full consenting process (Phase 2; see Figure 2 below) and the rest of the baseline surveys prior to being randomized. The same processes will occur at SCH if the potentially eligible patient does not have a current PAID-T available in their chart (i.e., within 12 months of the time of consent).

All potential participants who complete the PAID-T as part of the Phase 1 screening process (outside of their standard of care PAID-T) with the intention of enrolling in the study who do not subsequently meet the cut-off for enrollment will be given a \$5 gift card for their time. They will complete the PAID-T in the run in period via REDCap, verbally, or paper/pencil.

Protocol Version Number: 10

Protocol Version Date: 7/28/2021

[figure not shown]

Figure 2. Two-phase consenting flow chart.

20.2. Where the consent process will take place: In the diabetes clinic setting at both sites, the Clinical Research Center, or by phone/video.

Protocol Version Number: 10

Protocol Version Date: 7/28/2021

